### **9.10.5. Additional Efficacy Endpoints**

Additional efficacy endpoints will include CFB on the following endpoints:

- Muscle strength testing
- PUL entry item assessment
- PODCI Transfer and Basic Mobility scale

The analysis methods for these endpoints will be defined in the SAP. Additional efficacy endpoints may also be defined in the SAP.

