- f Per Investigator discretion, site calls may occur by telephone or use of other technology.
- g Randomization occurs after Screening assessments have been completed and eligibility is confirmed.
- h AEs and concomitant medication/therapy will be assessed at all visits and during site calls.
- i ECGs will be performed predose at all timepoints. At Week 26, ECG will be performed predose and 2 hours postdose ( $\pm 15$  min).
- j Cardiac monitoring will be performed for approximately 48 hours remotely via a wearable cardiac monitoring device if approved for use in the participating country.
- k Blood samples will be drawn in the morning when possible.
- l DNA sample may be collected at Baseline for drug metabolizing enzyme and/or transporter analysis as well as pharmacogenomic analysis of potential markers of clinical risk/benefit.
- m Assessments should be performed in the order listed and in the morning when possible. Time to stand from supine and 10MWT will be recorded as measured in the NSAA.
- n The PUL 6-point entry item scale will be performed at all timepoints. If a patient scores a 6 on the PUL entry item scale, no further PUL testing is required for the visit.
- o Videotaping at Baseline is required if Screening video did not pass QC.
- p PODCI will be performed when feasible.
- q These assessments should be collected within 2 months prior to Day 1. In Germany, bone assessment will not be performed until the respective approvals from the German Federal Office for Radiation Protection (Bundesamt für Strahlenschutz) become available.
- r Patient compliance with the nutritional guidance will be confirmed throughout the trial.
- s Urine PK collection will be performed at Week 13. Plasma PK collection will be performed predose at Week 13 and Week 52. At Week 26 plasma PK collection will be performed predose, 1 hour ( $\pm 5$  min), 2 hours ( $\pm 15$  min), and 4 hours ( $\pm 15$  min) postdose.

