2.6.3.2. Performance of Upper Limb (PUL) Entry Item Assessment

The PUL (PUL 2.0; [Pane \(2018\)](#)) was specifically designed to assess upper limb function in ambulant and non-ambulant DMD patients. The PUL is made up of a 6-point entry item assessment to define starting functional level, and 22 items subdivided into shoulder level (6 items), middle level (9 items), and distal level (7 items) dimension. Loss of full overhead reach occurs at median age 9.6 years with some boys losing the ability as early as age 5 or 6.

Patients will perform the PUL entry item assessment; based on the age of patients in this study, most patients are expected to score a 6 on the scale of 0 – 6 and will not be required to perform the additional items.

Patients who score below a 6 on the entry item assessment will perform a subset of the PUL battery including the shoulder level dimension and supination, consisting of 7 items with a maximum score of 14. Completion of the 6-point entry item assessment is expected to take approximately 5 minutes. Completion of the battery of PUL assessments is expected to take approximately 20 minutes. Any missing items on the entry item assessment or the subset of the PUL battery will be considered a zero for the purposes of deriving the overall score.

The following endpoints will be analyzed from the PUL assessments

- Item 1 and Item 2 (Summed): this is the sum of Items 1 and 2:
 - Item 1: Shoulder abduction both arms above head “Raise your arms out to the side and above your head– try and keep straight elbows” a 0 – 2 point scale

- Item 2: Raise both arms to shoulder height (elbows at shoulder height) “Raise your arms to shoulder level” a 0 – 2 point scale
- PUL Total Score: The PUL total score is a sum of items 1 -7. Each of the 7 items has a score range from 0 – 2 with a higher score indicating better function. The PUL total score ranges from 0 – 14 with a higher score indicating better functioning.

For patients who score a “6” on Item A (and are not required to perform PUL items 1 – 7), the following data imputation will be performed:

- Items 1 and 2 be imputed with a value of 2
- Items 3, 4, 5, 6, 7 will not be imputed, items will remain missing.
- The PUL Total Score will be not be imputed, the score will be missing.

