Due to this missing data issue, the analysis of the PUL Total Score will be performed on the subset of FAP patients who did not score a “6” on Item A. The analysis of Items 1 and 2 (i.e., where scores are imputed for patients who score a “6” on Item A) will be performed on the FAP.

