4.10.3. Additional Efficacy Analyses

Additional efficacy endpoints include CFB on the following:

- Muscle strength testing: 2 endpoints: elbow flexion (i.e., average of the left and right elbows), knee extension (average of the left and right knees). If either the left or right value is missing the value will be the non-missing score.

Note: values which are indicated as not being valid as determined by a response of “No” to “Was test valid? (i.e. representative of child’s true function)” for these assessments will not be included in the analysis (but will be presented in listings).

These additional efficacy endpoints will be analyzed using an MMRM ANCOVA, in a manner similar to that described in [Section 4.10.1](#) with the corresponding baseline muscle strength endpoint replacing baseline NSAA as a covariate.

- **PUL endpoints:** This includes the PUL Total Score, and the sum of individual items 1 and 2 (note these 2 items are imputed for patients who scored a “6” on Item A as defined in [Section 2.6.3.2](#)).

The sum of individual items 1 and 2, and PUL total score endpoints will be analyzed using an MMRM ANCOVA, in a manner similar to that described in [Section 4.10.1](#) with the corresponding baseline PUL score replacing baseline NSAA as a covariate.

PODCI Transfer and Basic Mobility Scale: This additional efficacy endpoint will be analyzed using an ANCOVA. The ANCOVA model will include CFB in the PODCI Transfer and Basic Mobility Scale at Week 52 as the dependent variable, treatment and region (North America vs. Europe/Asia/Australia) as factors, and baseline age (as a continuous variable), baseline time to stand from supine (as a continuous variable), and baseline PODCI Transfer and Basic Mobility Scale score (as a continuous variable) as covariates.

As an additional analysis of the PODCI Transfer and Basic Mobility Scale endpoint, the analysis above will be repeated subset to the subgroup of patients with the same caregiver completing the form at both baseline and Week 52 (i.e., from the PODCI eCRF page “Who completed this form?” with responses of: Caregiver, Father, Mother).

Note that summary statistics will be provided for the additional PODCI scales at each scheduled timepoint.

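### The SAP gives no defined analysis of the listed PUL entry-item endpoint, and the PUL Total change score exists only for boys below 6 both at baseline and at the later visit

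*SAP*

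**What the plan says.** Protocol 9.10.5 lists change from baseline in the "PUL entry item assessment" among the additional efficacy endpoints and leaves the method to the SAP: "The analysis methods for these endpoints will be defined in the SAP". SAP 2.6.3 repeats the endpoint.

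SAP 2.6.3.2 opens its list with "The following endpoints will be analyzed from the PUL assessments" and names two: the sum of Items 1 and 2, and the PUL Total (Items 1 to 7, range 0 to 14). SAP 4.10.3 gives both a repeated-measures model with the matching baseline PUL score as covariate, and nothing else: "This includes the PUL Total Score, and the sum of individual items 1 and 2".

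Item A acts as a gate. Under Protocol Appendix 1, "The PUL 6-point entry item scale will be performed at all timepoints", and after a 6, "no further PUL testing is required for the visit". For a boy scoring 6, SAP 2.6.3.2 sets Items 1 and 2 to 2 each and leaves Items 3 to 7 missing. As for the Total, "The PUL Total Score will be not be imputed, the score will be missing". The section then says that "the analysis of the PUL Total Score will be performed on the subset of FAP patients who did not score a" 6 on Item A, without saying at which visit, and that Items 1 and 2 are analysed on the FAP. It also counts missing PUL items as zero when the overall score is derived.

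SAP section 6 lists two changes from the protocol: the covariate terms in the main model and the rank-sum endpoint. PUL is not mentioned.

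**The concern.** There are two separate problems. First, the PUL endpoint that the protocol names is measured for every boy at every PUL visit, yet it reaches the analysis sections only as a skip rule and an imputation trigger. Two other PUL scores are modelled in its place, and the SAP does not say that this departs from the protocol.

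Second, whether a boy has a PUL Total at a visit depends on his Item A score at that visit. Item A is itself an upper-limb outcome that treatment may affect. A comparison restricted to boys still below 6 therefore conditions on something that happens after randomisation. If the drug helps boys reach 6, more active-arm than placebo boys drop out of the Total analysis, and they drop out because they did well. The observed-case model handles those absent values as missing at random.

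**Working it through.** The plan states no sample size, effect or power for any PUL endpoint, so there is no figure to reproduce. The check is a reading of the definitions, followed by illustrations on assumed inputs.

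**1. Item A through the documents**

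- Protocol 9.10.5: listed as an endpoint; method left to the SAP.
- SAP 2.6.3: listed as an endpoint.
- SAP 2.6.3.2: not among the PUL endpoints to be analysed.
- SAP 4.10.3: no model.
- SAP 4.10: a general sentence promises listings and summaries of efficacy endpoints by arm and visit where that applies. Item A is not named.
- SAP section 6: not declared as a change.

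**2. Who has a change score**

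| Item A at baseline | Item A at visit | Change in Total | Change in Items 1+2 |
|---|---|---|---|
| below 6 | below 6 | available | available |
| below 6 | 6 | none: visit Total missing | available (visit value 2 + 2 = 4) |
| 6 | below 6 | none: baseline Total missing | available (baseline value 2 + 2 = 4) |
| 6 | 6 | none | available (4 − 4 = 0) |

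The two lost groups differ in kind. Losing boys at 6 at baseline is a restriction fixed before treatment; it narrows the population but leaves a randomised comparison. Losing boys who reach 6 later is selection on outcome. The SAP does not say which visit defines the subset, but a baseline definition alone does not cure this, because the Total of a boy who later scores 6 is still left missing.

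**3. How few boys (shares at 6 are assumptions)**

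With 126 randomised and 20% dropout, 126 × 0.8 = 100.8 are evaluable. With share s at 6, m = 100.8 × (1 − s) remain. Power is from the noncentral t distribution with non-centrality 0.625 / √(3/m + 3/(2m)) and m − 2 degrees of freedom, two-sided 0.05, allocation 2:1. The 0.625 is borrowed from the NSAA assumption.

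| s | m | Power |
|---|---|---|
| 0.5 | 50.4 | 54% |
| 0.7 | 30.2 | 35% |
| 0.9 | 10.1 | 13% |

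These m are upper limits, since boys who later reach 6 and eteplirsen-treated boys (outside the FAP) also drop out.

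**4. Direction of the distortion (all inputs assumed)**

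A simulation used 400,000 boys per scenario, allocated 2:1. Latent baseline function has SD 1; change is −0.2 plus the treatment effect, with SD 0.6. Item A is 6 when latent function plus error (SD 0.3) passes a cut-off set so that 60%, 75% or 90% score 6 at baseline. The effect is estimated at one visit, adjusted for baseline.

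| At 6 at baseline | True effect | Below 6 at baseline, all Totals seen | Below 6 at both visits | Retained, active / placebo |
|---|---|---|---|---|
| 60% | 0.60 | 0.597 | 0.429 | 24.1% / 33.1% |
| 75% | 0.60 | 0.601 | 0.407 | 13.4% / 19.7% |
| 90% | 0.60 | 0.605 | 0.380 | 4.6% / 7.3% |
| 60% | 0 | −0.006 | −0.004 | 33.3% / 33.1% |
| 75% | 0 | −0.001 | −0.004 | 19.7% / 19.7% |
| 90% | 0 | 0.006 | 0.007 | 7.4% / 7.5% |

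With a true effect, the estimate shrinks and retention differs between arms. With none, both distortions essentially vanish.

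**The case against.** The strongest reply is that the SAP already covers most of this. It presents the Total restriction openly, as the consequence of a skip rule. It also provides a PUL analysis on the whole FAP: with Items 1 and 2 set to 2 when Item A is 6, a boy who falls from 6 has a baseline value and a boy who rises to 6 keeps his later one. PUL lies outside the testing hierarchy in SAP 4.2.5 and outside the rank-sum score. All of that stands and limits the weight of the point.

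Four stronger readings are tempting but not supported:

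- A reader might infer that the entry item will go unreported. The general sentence in SAP 4.10 could still produce a listing or descriptive table; what is absent is a defined analysis.
- A reader might infer that every decline among boys starting at 6 is lost. That is true of the Total only. Items 1 and 2 can register such a decline if either scores below 2.
- A reader might infer that the largest improvers are removed. Removal depends on reaching the ceiling: a boy going from 5 to 6 is dropped, one going from 2 to 4 is kept.
- A reader might infer a false-positive risk or a known bias. The illustration shows no material bias under a null effect, and its attenuation rests entirely on assumed inputs.

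Two obvious repairs also fail. The main repeated-measures model suits Item A poorly, because it is ordinal and most boys are expected to sit at its top score. Crediting a later 6 with the maximum Total would impute Items 3 to 7, which the SAP deliberately leaves missing.

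**Conclusion.** The point holds in limited form. A listed endpoint has no specified model, test or named summary, and the omission is not declared. The Total's change score is confined to boys below 6 at both baseline and the visit, which conditions on a post-randomisation outcome and can attenuate an effect and unbalance retention. These conclusions follow from the definitions and need no assumption.

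The size cannot be quantified from the documents, which give neither the share at 6 nor the number expected to reach it. The figures above show direction only. The analysis of Items 1 and 2 on the FAP partly mitigates the problem. The priority is low: no primary or secondary conclusion depends on PUL.

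**What to change.** 1. Specify an analysis of Item A on the FAP that suits its ceiling: for example an ordinal model, or the proportion by arm declining from 6 at Week 52 among boys at 6 at baseline.
2. Define the PUL Total subset by baseline Item A below 6, report by arm how many later reach 6, and label the Total analysis descriptive rather than a randomised comparison.
3. Limit the zero rule in SAP 2.6.3.2 to boys required to perform the items. As worded, it conflicts with leaving Items 3 to 7 and the Total missing for boys at 6. It also names the entry item, so state how a missing Item A is handled.
4. Record the departure from Protocol 9.10.5 in SAP section 6.

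The cost is one added analysis, some SAP wording, and a Total result that carries no inferential claim. No new data are needed, since Item A is already collected at every PUL visit.

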2.6.3.3. Pediatric Outcomes Data Collection Instrument (PODCI)

The PODCI is an assessment of health-related functioning in children, and is designed to be completed by the parent/caregiver of children aged 10 or younger ([Henricson, 2013](#)). It contains 86 questions, takes approximately 20-30 minutes to complete, and provides information on the following 6 scales:

- Upper Extremity and Physical Function Scale – measures difficulty encountered in performing daily personal care and student activities
- Transfer and Basic Mobility Scale – measures difficulty experienced in performing routine motion and motor activities in daily activities
- Sports and Physical Functioning Scale – measures difficulty or limitations encountered in participating in more active activities or sports
- Pain/Comfort Scale – measures the level of pain experienced during the past week
- Happiness Scale – measures the overall satisfaction with personal looks and sense of similarity to friends and others of own age
- Global Functioning Scale – a general combined scale calculated from the first 4 scales listed above.

For each of the first five scales, the average of the scores in the questions is calculated and standardized on a 0 to 100 scale, where higher numbers represent a positive value. The global functioning scale is an average of the first four subscales (i.e., excluding the “Happiness Scale”). The details of the PODCI scoring are provided in [Appendix 3: PODCI Scoring Algorithm](#).

2.6.3.4. Multivariate Rank Sum Score Endpoint

This multivariate rank sum score endpoint is designed to assess the effect of edasalonexent versus placebo across multiple endpoints using a non-parametric rank-based approach. For Week 52, the endpoint is the sum of the ranks of the following Week 52 CFB scores: NSAA,

10MWT speed, stand from supine speed, 4-stair climb speed, and PODCI transfer and basic mobility scale.

The multivariate rank sum score at Week 52 will be derived using the method described in [O'Brien \(1984\)](#). Specifically, for each patient i , the overall rank score is given by:

$$R_{ii} = r_{ij1} + r_{ij2} + r_{ij3} + r_{ij4} + r_{ij5}$$

where:

i = an indicator for a specific patient

j = an indicator for a treatment group

r_{ij1} = patient i 's rank of the Week 52 CFB in NSAA score at Week 52

r_{ij2} = patient i 's rank of the Week 52 CFB in 10MWT speed score at Week 52

r_{ij3} = patient i 's rank of the Week 52 CFB in Stand from Supine Speed score at Week 52

r_{ij4} = patient i 's rank of the Week 52 CFB in 4-stair Climb Speed at Week 52

r_{ij5} = patient i 's rank of the Week 52 CFB in the PODCI Transfer and Basic Mobility Scale score at Week 52 (described in [Section 2.6.3.3](#))

In determining ranks, if there are ties, the average value of the ranks that would have been assigned to all observations with the same value will be used.

Only patients with non-missing values for each of these 5 Week 52 CFB scores will be included in the analysis.

The patient's baseline rank sum score will be used a covariate for some of the rank-based analyses. This is defined as the sum of the ranks across the 5 endpoints using the baseline value (using the methodology described above).

2.6.4. Safety Endpoints

Safety will be evaluated in terms of all treatment-emergent adverse events (TEAEs) and serious adverse events (SAEs), as well as physical examination, growth parameters (height and weight), vital signs, clinical laboratory parameters (including chemistry, hematology and urinalysis), adrenal function (adrenocorticotrophic hormone (ACTH) and cortisol levels), and electrocardiogram (ECG). Data from ECGs will be locally read and centrally evaluated. Cardiac monitoring and bone evaluations will also be performed.

2.6.5. Additional Endpoints

To assess acceptability and palatability of edasalonexent, caregivers will complete a study drug questionnaire, these results will be presented in a listing and the following questions will be summarized by treatment group.

- 1) The taste and aftertaste (a taste that remains in your mouth after swallowing) of the study drug capsules are acceptable.
- 2) The smell of the study drug capsules is acceptable.
- 3) The size and shape of the study drug capsules are acceptable:

These 3 questions are measured on a 1 (strongly agree) to 5 (strongly disagree) point scale. The frequency of each response category will be summarized.

3. PATIENT POPULATIONS

3.1. Population Definitions

The following patient populations will be evaluated and used for presentation and analysis of the data:

- Randomized Population: all patients who are randomized into the study with patients to be analyzed based on the study treatment they were randomized to.
- Safety Population: all patients who receive at least one dose of study drug with patients to be analyzed based on the actual study treatment received.
- Full Analysis Population (FAP): all patients in the Randomized Population who receive at least one dose of study drug and provide at least one non-missing post-Baseline NSAA efficacy assessment.
 - Note that the FAP will exclude patients on eteplirsen at randomization and patients will be analyzed based on the study treatment they were randomized to.
- Per Protocol (PP) Population: all patients in the FAP who complete the 52-week treatment period of the study without any significant protocol deviations with patients to be analyzed based on the study treatment they were randomized to.

The set of patients in the Per Protocol population may be updated due to study drug compliance information which will not be collected until after database lock and unblinding due to the COVID-19 pandemic, see [Section 3.2](#).

note: the variable to determine a patient completing the 52-week treatment period is from the End of Study eCRF page “Did subject complete the study?” = Yes.

The FAP will be the primary population for the analysis of efficacy parameters. The Safety Population is the primary population for the analysis of safety endpoints.

Note that if siblings are enrolled, only one sibling will be included in the Randomized Population. This is to avoid having siblings being randomized to different study medications, increasing the risk a subject will inadvertently take incorrect study medication. The second sibling will be assigned to the same treatment group as the randomized sibling. If both siblings meet the inclusion/exclusion criteria, the sibling to be included in the Randomized Population will be the first sibling randomized, both siblings will be included in the Safety Population (see [Section 3.1](#)). The sibling not included in the Randomized Population will have their data presented in the listings and will be included in some of the sensitivity analyses.

3.2. Protocol Deviations

At the discretion of the sponsor, significant protocol deviations as determined by a review of the data prior to unblinding of the study may result in the removal of a patient’s data from the Per Protocol Population. The sponsor, or designee, will be responsible for producing the final protocol deviation file (formatted as a Microsoft Excel file), in collaboration with Cytel and the data monitoring group as applicable; this file will include a description of the protocol deviation, and clearly identify whether or not this deviation warrants exclusion from the Per Protocol Population. This file will be finalized prior to database unblinding.

All protocol deviations will be summarized by category and presented in the data listings. The following are the protocol deviation categories:

- Eligibility
- Inclusion/Exclusion criteria
- Informed consent deviation
- Laboratory
- Other
- Outside protocol window
- Procedure or labs not done
- Restricted concomitant medication change
- Study drug
- Study drug dosing
- Study procedures
- Subject non compliance
- Visit not done
- Visit window

Note: Due to the impact of the COVID-19 pandemic on study sites and patients, drug accountability may be incomplete for some patients at the time of database lock and the timeframe for resolution may not be near term or indeed possible. This impacts the assessment of study drug compliance. If, after database lock and unblinding, additional drug accountability information is provided such that a patient's overall study drug compliance is determined to be less than 80%, then the Per Protocol population will be updated to exclude this patient (i.e., if the patient has not previously been excluded from the Per Protocol population). This set of patients (i.e., patients with less than 80% study drug compliance identified after database lock and unblinding) will be provided in the CSR.

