4.10.4. Sensitivity Analyses for the Primary Efficacy Endpoint

The following sensitivity analyses of the primary and secondary efficacy endpoints will be performed to assess the robustness of the analyses across endpoints:

a) The primary efficacy endpoint analysis performed on the PP population

The primary efficacy endpoint analysis, as defined in [Section 4.10.1](#) will be performed using the PP Population

b) The primary efficacy endpoint analysis performed on the Randomized population

The primary efficacy endpoint analysis, as defined in [Section 4.10.1](#) will be performed using the Randomized Population (note: this includes randomized patients on eteplirsen)

c) ANCOVA on the primary efficacy endpoint using MAR, MNAR, and OC

The primary efficacy endpoint, the CFB in the NSAA Total Score at Week 52 will be analyzed by an ANCOVA model. The ANCOVA model will include CFB in the NSAA Total Score at Week 52 as the dependent variable, treatment and region (North America vs. Europe/Asia/Australia) as factors, and baseline age (as a continuous variable), baseline time

to stand from supine (as a continuous variable), and baseline NSAA score (as a continuous variable) as covariates.

Three different methods of addressing missing data will be performed:

- 1) **Missing at Random (MAR)** Missing data will be imputed using the MAR algorithm described in [Section 4.10.6.1](#).
- 2) **Missing Not at Random (MNAR)** Missing data will be imputed using the MNAR algorithm described in [Section 4.10.6.2](#).
- 3) **OC (Observed Case)** this ANCOVA will be performed on non-missing data.

These analyses will be performed on the FAP.

d) Observed Week 52 MMRM

The primary efficacy endpoint analysis will be repeated (i.e., as described in [Section 4.10.1](#)) subset to those patients who had a non-missing CFB value at Week 52.

e) MMRM with multiple imputation assuming MAR

The primary efficacy endpoint analysis will be repeated (i.e., as described in [4.10.1](#)) with missing data imputed based on a Missing at Random (MAR) pattern as described in [4.10.6.1](#).

f) MMRM with multiple imputation assuming MNAR

The primary efficacy endpoint analysis will be repeated (i.e., as described in [4.10.1](#)) with missing data imputed based on a Missing Not at Random (MNAR) pattern as described in [4.10.6.2](#)

g) Including siblings

The primary efficacy endpoint analysis will be repeated (i.e., as described in [4.10.1](#)) including the siblings in the FAP.

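### The Per Protocol Population can be reduced after unblinding on late drug accountability data, and the SAP does not commit to reporting the analysis on the set fixed at lock

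*SAP*

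**What the plan says.** SAP 3.2 first gives the usual rule. Deviations that remove a patient from the Per Protocol Population are identified in a data review before unblinding and entered in a deviation file. Of that file it says: "This file will be finalized prior to database unblinding".

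A closing note then makes an exception. Because of the pandemic, drug accountability may be incomplete for some patients at lock, and "the timeframe for resolution may not be near term or indeed possible". If "after database lock and unblinding, additional drug accountability information is provided" and shows that a patient's "overall study drug compliance is determined to be less than 80" percent, "then the Per Protocol population will be updated to exclude this patient". The patients removed this way are to be identified in the clinical study report.

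SAP 3.1 carries the same exception in the population definition: "The set of patients in the Per Protocol population may be updated due to study drug compliance information". It gives the pandemic as the reason why some of these data will reach the sponsor only once the codes are open.

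The set is used in SAP 4.10.4, item (a): "The primary efficacy endpoint analysis performed on the PP population". SAP 4.10.5 extends the 4.10.4 analyses to the three secondary endpoints.

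**The concern.** A Per Protocol analysis is useful as a check on the primary result when its membership is settled before anyone can see how membership affects the answer. The exception departs from that. The rule says what happens once a count is in. It does not say which missing counts are pursued, who reconciles them, or when the work stops, and some of this falls after unblinding.

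If only the updated set is reported, the reader sees a list of late removals but no estimate, interval or p-value for the set fixed at lock. The reader then cannot tell whether the Per Protocol conclusion depended on those removals. What is at stake is the credibility of four sensitivity analyses.

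**Working it through.** **1. What is fixed in advance.**
- Trigger: overall compliance below 80% (SAP 3.2).
- Formula: 100 × actual capsules / planned capsules, with planned capsules built from the daily count and the days in each dispensing period (SAP 4.9).
- Convention for missing kits: a kit not at the site, with no return date and not recorded as damaged by the subject, counts as 90 capsules used (SAP 4.9).
- Timing: the exception entered in SAP version 5, dated 5 October 2020 (SAP 1.2.4). Protocol 9.1 requires the SAP to be final before lock and unblinding.

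**2. What is left open.**
- Cut-off date for late accountability data: none in SAP 3.1, 3.2 or 4.9.
- Blinding of those who reconcile counts: not required. SAP 2.3 and Protocol 5.5.2 keep site staff, monitors, investigators and the sponsor blinded until results are available. That covers some late counts, but not those arriving after results are out.
- Reporting on the set fixed at lock: no commitment.

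**3. Direction of the update.** The note provides for exclusion only. This largely follows from the kit convention. A kit already counted as 90 used can only be revised downward, so for such kits a late count can lower compliance but not raise it.

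**4. How far a late count can move a patient.** Assume body weights of 15, 20 and 30 kg, 250-mg capsules, 100 mg/kg/day and 364 days, with kits of 90.

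| Weight (assumed) | Capsules/day | Planned capsules | Effect of one kit | Untaken capsules to fall from 100% to 80% |
|---|---|---|---|---|
| 15 kg | 6 | 6 × 364 = 2184 | 90/2184 = 4.1 points | 437 (4.9 kits) |
| 20 kg | 8 | 8 × 364 = 2912 | 90/2912 = 3.1 points | 582 (6.5 kits) |
| 30 kg | 12 | 12 × 364 = 4368 | 90/4368 = 2.1 points | 874 (9.7 kits) |

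A patient counted as fully compliant at lock needs about five to ten kits' worth of untaken capsules to be removed. A patient a few points above 80% at lock can be removed on one kit.

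**5. Analyses affected.** One under 4.10.4(a) plus three under 4.10.5 makes four. The primary analysis uses the Full Analysis Population (SAP 3.1), and the hierarchy in SAP 4.2.5 does not use the Per Protocol set.

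**6. Illustrative size.** The plan gives no figure to reproduce, and the number of open cases is not stated. Inputs: 126 patients, 2:1, about 20% dropout, SD 4.8 and design difference 3.0 (SAP 4.1).
- Remaining: 126 × 0.8 = 100.8, about 67 and 34.
- SE of the difference: 4.8 × √(1/67 + 1/34) = 1.01 points.
- Suppose k edasalonexent patients are removed late, averaging 1 SD below their arm mean (assumption). The arm mean moves by k × 4.8/(67 − k):
  - k = 2: 9.6/65 = 0.15
  - k = 5: 24/62 = 0.39
  - k = 10: 48/57 = 0.84
- Two placebo patients on the same assumption: 2 × 4.8/(34 − 2) = 0.30.

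These are differences in simple means, not output of the repeated-measures model. The counts of 67 and 34 are not Per Protocol counts. That set also leaves out eteplirsen users and patients with significant deviations, so its arms would be smaller and each removal would weigh slightly more.

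**The case against.** The strongest reply is that the update rule is itself pre-specified. The threshold is numerical and the formula is written out. The exception is labelled in 3.2, cross-referenced in 3.1 and declared in the change history, and its cause is a real pandemic problem. No passage describes the sponsor choosing which counts to chase. The late exclusions are to be identified in the study report, so the set at lock can be rebuilt. Freezing the set also has a cost, since it may keep patients known to be below 80%, whom a Per Protocol set is meant to leave out.

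Most of this stands, and it rules out three stronger readings that a reader might infer:
- *Membership is decided by judgement with the codes known.* The documents do not support this, because exclusion follows automatically once compliance is below 80%.
- *SAP 3.2 contradicts itself.* It states a general rule and then an explicit exception.
- *The set fixed at lock is lost.* Identification in the study report allows it to be reconstructed.

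The reply does not remove two gaps. A fixed threshold does not determine which late counts reach it or when collection stops. Identifying the removed patients also does not report the result on the set at lock.

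**Conclusion.** The point holds in a narrow form. The SAP allows the Per Protocol Population to shrink after unblinding under a fixed 80% rule, leaves the pursuit and end date of late counts open, and does not promise the result on the set at lock.

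The size is unknown, because the number of patients concerned is not given. On the assumptions above, two late removals would shift the difference by 0.15 to 0.30 point, and ten from the edasalonexent arm by 0.84, against a standard error of about 1.0 and a design difference of 3.0. A few removals would matter little; ten would not be trivial. These figures assume that every removed patient lies on the same side of the arm mean, which nothing in the documents suggests.

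A reader might infer that the primary result is exposed. It is not. This is an inexpensive improvement to four supporting analyses, and it implies no misuse.

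**What to change.** Amend SAP 3.1 and 3.2 so that the Per Protocol Population is frozen at database lock on the compliance data then available, and use that set for 4.10.4(a) and the three counterparts under 4.10.5. Report the set updated with later accountability beside it as an additional analysis, labelled as based on data received after unblinding. It would also help to name a cut-off date for late accountability data and to have counts reconciled by staff who do not know the allocation.

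The cost is SAP wording and up to four extra runs of existing code, one per endpoint. The drawback is that the frozen set may include a few patients later shown to be below 80%; the side-by-side analysis shows what difference they make, so no information is lost.
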